7.2 Safety Review Committee

A Safety Review Committee (SRC) will be convened and will include the medical monitor, the safety manager(s), clinical monitor(s) and clinical manager. The SRC will oversee safety data

(AEs, vitals, clinical labs, ECG data, etc.) generated by enrolled study subjects on the trial. In addition, they will review all SAEs and UADEs and clinically significant safety observations noted during the study. Oversight work and study related decisions will be performed in accordance with a written Safety Review Committee Plan.

8 Information for the Investigator: Potential Risks of the Device

Adverse events that may be anticipated in this clinical study are outlined for the investigational drug and the MediBeacon[®] Transdermal GFR Measurement System.

8.1 Investigational Drug

Clinical data from the Pilot 1A and 1B studies (total n = 32 subjects) included the following adverse events:

- Pilot 1A (n = 16)
 - Vasovagal reaction (1 subject)
 - Dizziness (1 subject, 2 events)

These events occurred in fasting subjects shortly after dosing and resolved on that day. No other AEs, injection site reactions, clinically significant laboratory values or significant changes in vital signs were noted during this study.

- Pilot 1B (n = 16)
 - Headaches (56.3% of subjects)
 - Erythema (at the site of the adhesive) (100% of subjects)
 - Diarrhoea (1 subject)
 - Dizziness (occurring in 1 subject following release from the study center)

Erythema was thought to be related to the adhesive used to adhere the sensor to the skin. Headaches were deemed related to the head strap required to hold the forehead sensor in place. Sensor placement on forehead was discontinued post Pilot 1B.

MB-102 is excreted in the urine. Therefore, urine discoloration (chromaturia) is expected but has not been considered an adverse event in prior studies.

In the Pilot 2 study, a total of 234 subjects with normal to compromised renal function have been exposed to MB-102. A total of 120 subjects received a dose of 4 μ mol/kg followed by a 5 mL injection of iohexol. Seventy (70) subjects received a single dose only (no iohexol) of 4 μ mol/kg of MB-102) and 44 have received a fixed dose of 130 mg (7 mL). All reported AEs were mild or moderate in severity and resolved without sequalae. Overall, MB-102 given in conjunction with or without iohexol was well tolerated in this subject population.

A total of 40 adverse events were reported in 28 treated subjects in Groups 1, 2 and 3 for an AE rate of 12.0% in the treated population. A total of 31 events were considered mild and 9 moderate events occurred in 5 subjects (2.5% of the population). There were no severe events

reported. There were no Serious Adverse Events (SAEs) reported during the study. There were no Unanticipated Adverse Device Effects (UADEs) reported during the study.

Four AEs, dyspepsia, chromaturia, hot flush and (facial) rash were considered related to investigational product (MB-102); all events resolved by study completion. Dyspepsia and chromaturia were also considered to be related to iohexol. Of note, chromaturia is an expected effect of MB-102 (noted in the Investigator's Brochure) and expected in all subjects as the excretion of MB-102 will color the urine of subjects receiving the product. It is not a documented effect of iohexol (per the label).

Seven (7) AEs occurring in 7 subjects were considered related to the device (sensor attachment); these included application site erythema, dermatitis, and pruritus and were considered related to the adhesive material used to hold the sensor in place. Two events of application site discoloration (melanin spot at the sensor location) were noted in 2 subjects in the SOG cohort which resolved within 24 hours of removal of the sensor. Other reported AEs (conjunctivitis, nausea, vomiting, cardiac murmur, headache, anxiety, micturition urgency, pollakiuria, urine odor abnormal, peripheral oedema, fatigue, and a pruritis event [not at the sensor location] were considered not related to MB-102, the sensor device or iohexol. Injection site reactions (bruising, erythema, extravasation) were also not considered related to MB-102.

There may also be other risks that are unforeseen at this time. For additional information on the risk profile, please reference the current Investigator's Brochure.

8.2 MediBeacon[®] Transdermal GFR Measurement System

There are no direct risks associated with the MediBeacon[®] Transdermal GFR Measurement System (monitor portion) as it does not contact the study subject. Adverse events observed from the sensors are with regard to the methods used to affix it to the study subject. Risks may include a reaction to the sensor or adhesive material or the adhesive used on the skin clip.

8.2.1 Adhesive Clip

As with the adhesive used on the sensors, there is the chance of reaction to the adhesive used to attach the clip to the skin. Reactions could include redness, itchiness or other localized skin reactions. Clips will be provided, however other means (surgical tape, tegaderm, etc.) to secure the sensor cord may be used.

8.3 Trial Procedures

Blood collection may lead to light-headedness and dizziness in some study subjects. It is recommended to ensure subjects continue to hydrate and eat during the dosing day to mitigate the effect of blood loss.

Bruising and pain at the site of the venous catheters may also be expected.

8.3.1 Dose Extravasations

Should a dosing extravasation occur, a subject may report pain or burning during the injection. Subjects should be queried during the injection regarding any sensation. Subjects with MB-102 or saline extravasations will be discontinued from PK collection and fluorescent measurements but continued in the study for safety. All extravasations will be collected as adverse events and protocol deviations.

9 Statistical Methods

9.1 Overview

The transdermal-derived GFR data (tGFR) is obtained directly from the MediBeacon[®] Transdermal GFR Measurement System (TGFR) for each subject. This tGFR value is compared to the subject's nGFR_{BSA} for the study endpoint determination.

9.2 Analysis Populations

The following analysis populations will be defined for the study:

- Intent-to-Measure (ITM) Population The ITM population will consist of all subjects who are enrolled in the study in Stratum 1 & 2 and for whom an end of session tGFR has been calculated, and who have not had any major protocol deviations.
- Modified Intent-to-Measure (mITM) Population The mITM population will consist of all subjects in the ITM population with no outlier PK parameters.
- Safety Population The safety population will consist of all subjects who are enrolled in the study and have been dosed with MB-102.
- Pharmacokinetic (PK) Population The pharmacokinetic population will consist of all subjects who are enrolled in the study and have any PK data.

The mITM population will be the primary analysis set for all effectiveness analyses. The Safety Population will be used for the analysis of all safety variables and baseline characteristics. The PK Population will be used for the analyses of PK data.

9.3 Subject Disposition

The number and percentage of subjects who complete the study or who terminate early from the study and the reasons for early termination will be collected and reported. Subjects will be considered to have completed the study if they complete the dosing day.

The number and percentage of subjects in each analysis population will be presented. Percentages will be based on the number of subjects enrolled.

9.4 Plasma Pharmacokinetic Analyses

The pharmacokinetic objective is to characterize the single dose pharmacokinetics of MB-102

following IV bolus dosing, specifically, to obtain the clearance and total volume of distribution of MB-102 using compartmental methods in Phoenix WinNonlin (Certara, Version 8.1 or higher).

Based on prior data, it is expected that a two-compartment model will adequately describe the pharmacokinetic profiles of MB-102. The following two-compartmental pharmacokinetic parameters will be determined:

- \triangleright C_{max}: The maximum plasma concentration.
- > AUC: Area under the plasma concentration-time curve
- > $t_{1/2\alpha}$: Half-life associated with distribution phase
- > $t_{1/2\beta}$: Half-life associated with elimination phase
- > $t_{1/2}$: elimination half-life from central compartment.
- V: Total volume of distribution
- > CL: Systemic clearance
- ➢ V1: Volume of distribution for central compartment
- > V2: Volume of distribution for peripheral compartment

The two key PK parameters from compartmental analysis are CL and V. The clearance (CL) derived from the two-compartment model is the plasma-derived GFR used to calculate the BSA indexed nGFR that is the comparison to the tGFR for the P30 calculations. V is used in the calculation of GFR indexed to volume of distribution.

All PK concentrations and parameters will be listed. As each subject will have a unique GFR measurement, summary statistics are not applicable in this analysis.

Individual figures will be provided for plasma PK concentrations. All figures will be produced on both linear-linear and logarithmic- linear scales with data and the two-compartment fit.

9.5 Primary Endpoint Analysis

The primary endpoint is the performance measure of P30 for transdermal-derived GFR with respect to the plasma-derived indexed GFR, with a 95% confidence interval. The performance goal is 85%. Success for the study will be that the lower limit of the 95% CI is greater than 85%.

9.6 Safety Analyses

Safety of MB-102 will be evaluated through treatment emergent adverse events (TEAEs), where treatment emergence is defined with respect to the first dose of MB-102.

Safety of the MediBeacon[®] Transdermal GFR Measurement System will be evaluated through TEAEs, where treatment emergence is defined with respect to the start time of Transdermal GFR Measurement System use (placement of the sensor on the skin).

Additional safety variables include physical examinations, clinical laboratory assessments, ECGs, and concomitant medication use.

All safety analyses will be done for subjects receiving a single dose of MB-102.

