- 1. Concomitant medications administered within 3 days prior to baseline through the final follow-up visit will be recorded.
- m. Adverse events are collected from the time of sensor placement (for baseline measurement) through the follow-up visit.
- n. Fitzpatrick Skin Scale will be assessed by evaluating the skin on the upper chest (where sensors will be placed).

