7.1.2 Safety Assessments

Safety will be monitored by the assessments described below as well as the collection of AEs at every visit after screening. Planned safety assessments are detailed in the MediBeacon[®] Transdermal GFR Measurement System Study Schedule (**Table 2**). The investigators or site staff will be responsible for monitoring the safety of subjects who have entered this study and will be responsible for detecting, documenting and reporting events that meet the definition of an adverse event (AE) or serious adverse event (SAE). Significant findings that were noted to be

present at or prior to dosing must be included in the relevant medical history page of the eCRF. Significant new findings that begin or worsen after dosing must be recorded on the AE page of the eCRF. Subjects should be followed until the event is resolved or stabilized. AEs are collected from the time of initial sensor placement until the completion of the follow-up visit.

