7.1.2.8 Physical Examinations or Limited Physical Assessments

Physical examinations (when conducted by a physician, or other medically qualified investigator) or limited physical assessments (when performed by a nurse or other qualified individual) should include at a minimum an assessment of the head, ears, eyes, nose, throat (HEENT), respiratory, cardiovascular, and gastrointestinal systems. It is preferred that the same medical professional perform the baseline and post dosing assessments. Significant findings that were present prior to dosing must be included in the Medical History eCRF page. Significant new findings that begin or worsen after dosing must be recorded on the AE page of the eCRF.

Clinically significant abnormalities occurring post-dose should be evaluated by a physician and noted as AEs.

The study investigator will assess the subject for the occurrence of clinically significant new findings that begin or worsen after dosing which must be recorded as an AE on the eCRF page. A full physical exam should be conducted at screening and limited physical assessments may be conducted at other time points and must also be inclusive of the relevant organ or body system of interest for assessing the AE

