9.6.2 Physical Examinations/Limited Physical Assessments

The results of physical examinations will be collected as adverse events if clinically significant or as medical history (if observations are noted prior to TGFR start). Physical exam data will not be listed.

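### Device adverse events are counted from sensor placement, but the only safety set requires MB-102 dosing and one recording rule cuts off at dosing (low priority)

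*Combined protocol and SAP*

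**What the plan says.** Section 9.6 sets two clocks. MB-102 TEAEs run from the first dose. Device TEAEs are those "where treatment emergence is defined with respect to the start time of Transdermal GFR Measurement System use (placement of the sensor on the skin".

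Collection of adverse events follows the device clock. Table 2 legend m: "Adverse events are collected from the time of sensor placement (for baseline measurement) through the follow-up visit". Section 7.1.2: "AEs are collected from the time of initial sensor placement until the completion of the follow-up visit".

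The analysis set follows the drug clock. Section 9.2: "The safety population will consist of all subjects who are enrolled in the study and have been dosed with MB-102", and "The Safety Population will be used for the analysis of all safety variables and baseline characteristics". Section 5.4.5 also ties inclusion in the safety analysis to MB-102 exposure. No set is defined by device exposure.

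The rules for choosing between the AE page and medical history are split. Section 7.1.2 says that significant findings "present at or prior to dosing must be included in the relevant medical history page of the eCRF", and puts new findings on the AE page if they begin or worsen after dosing. Section 7.1.2.8 repeats this for examinations: "Significant findings that were present prior to dosing must be included in the Medical History eCRF page". Section 9.6.2 instead treats examination findings "as medical history (if observations are noted prior to TGFR start".

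**The concern.** Device safety is one of the stated objectives (section 4), and 9.6 deliberately opens the device window earlier than the drug window. That is sensible. Section 7.1.2.1 counts the adhesive pads as part of the device, section 8.2 names skin reaction to the adhesive or sensor as the device risk, and section 8.1 attributes all seven device-related AEs in Pilot 2 (seven subjects) to the adhesive. Such a reaction needs only a sensor on the skin, not an injection.

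If the analysis set and the recording rule both start at dosing, an event that 9.6 counts as a device TEAE can fail to reach the device-safety table. It may happen to a subject outside the set, or it may have been entered as medical history. What is at stake is the completeness of that table and the match between its numerator, its denominator and its own definition.

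**Working it through.** There is no figure to reproduce. The check sets the boundaries side by side.

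| Rule | Where | Boundary |
|---|---|---|
| Device TEAE starts | 9.6 | sensor placed |
| AE collection starts | Table 2 legend m, 6.5, 7.1.2 | sensor placed |
| Examination finding is medical history | 9.6.2 | before TGFR start |
| Significant finding is medical history | 7.1.2, 7.1.2.8 | present before dosing (7.1.2: at or before) |
| New finding goes on the AE page | 7.1.2, 7.1.2.8 | begins or worsens after dosing |
| Subject is in the Safety Population | 9.2 | has been dosed |

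**How far apart the boundaries are.** Table 2 legend g has the sensor on and the system started at least 15 minutes before dosing. The two boundaries therefore differ by at least 15 minutes, and by more if the baseline is re-started.

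**Case 1: sensor placed, no dose given.** The device clock in 9.6 has started and AEs are being collected. The subject is not in the 9.2 Safety Population, and that set is used for all safety variables, so a device event in this subject enters no safety table. Can this happen? No section describes such a subject. But 6.5 lists placement of the dosing catheter after sensor attachment and after AE collection has begun, and 6.6 then requires a patency check before injection. Section 5.4.4 allows withdrawal at any time. A failed catheter or a withdrawal in that interval would leave a subject with device exposure and no dose. This route is inferred from the listed order of procedures.

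**Case 2: dosed, with a skin reaction between placement and injection.** Sections 5.5.1 and 7.1.2.5.1 both provide for replacing a sensor before dosing, and the skin under the pad can be seen at that moment. Under 9.6, legend m and the collection window in 7.1.2, the reaction is a device AE. Under the findings rule in 7.1.2 it was present before dosing and so is medical history, reaching the AE page only if it worsens after dosing. Section 7.1.2 therefore gives both answers within one paragraph. A site that follows only the findings rule keeps the event out of the TEAE tables.

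**Section 7.1.2.8.** The wording is the same as in 7.1.2, but the effect is slight. Section 6.5 lists the pre-dose assessment before sensor attachment and bars other procedures during baseline acquisition, and Table 2 schedules the next examination at the follow-up visit. No scheduled examination falls between placement and dosing.

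**The case against.** The strongest reply is that Case 1 is hypothetical. Section 6.5 lists the eligibility review, ECG, pregnancy test and laboratory draw before the sensor goes on, so most reasons not to dose should surface first. After a pre-dose displacement, 7.1.2.5.1 says to fit a new sensor and re-start, which is firmer than the permissive wording in 5.5.1. A safety set of dosed subjects is also defensible for a combination product whose device works only with the drug. All of this stands as an argument that the numbers are small. It does not supply an analysis set for a device event in an undosed subject.

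On Case 2, four of the relevant statements agree on sensor placement or TGFR start, and nothing says that a medical-history entry rules out an AE entry. Skin under an attached pad is mostly hidden until removal, which is normally after dosing. This also narrows the point, in practice to pre-dose sensor replacement. It does not remove the contradiction inside 7.1.2, whose instruction for the AE page is tied to findings after dosing.

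Three stronger readings are tempting and not supported.

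- A reader might infer that device events before dosing go unrecorded. They do not: collection starts at sensor placement, 7.1.2.5 has device observations and adhesive failures entered in the eCRF, and the committee in 7.2 oversees AEs.
- A reader might take the undosed back-up subjects in 6.11 as proof that Case 1 will occur. The protocol does not say that they wear a sensor.
- A reader might infer from the closing line of 9.6, which speaks of a single dose, that subjects re-dosed under 6.11 are excluded. That line describes the regimen, and 9.2 and 5.4.5 include everyone dosed.

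**Conclusion.** The mismatch is real and of low priority. The Safety Population in 9.2 and the findings rule in 7.1.2 do not cover the whole period that 9.6 assigns to the device, so a device event before dosing can be missing from the device-safety tables. It need not be, since other text supports recording it as an AE.

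No magnitude is claimed. The documents do not say how many subjects will have a sensor placed without being dosed, or a skin finding between placement and injection; either number may be zero. The effect is confined to the safety tables and their denominators. The primary endpoint, SAE reporting and safety committee review are unaffected.

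The conclusion rests on two assumptions: that 9.2 is the complete list of analysis sets, and that sites may follow the findings rule in 7.1.2 as written. Section 9.6.3 leaves laboratory details to an SAP. If an SAP defines a device-exposed set, Case 1 falls away and Case 2 remains.

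**What to change.** 1. In 9.2 and 9.6, define a set of all subjects with a sensor placed and use it for device TEAEs. Keep the existing Safety Population for MB-102 TEAEs.
2. In 7.1.2, use sensor placement/TGFR start as the single cut-off between medical history and the AE page, as 9.6.2 already does. Make the same change in 7.1.2.8 for consistency. The first-dose clock for MB-102 TEAEs does not change.

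No new data are needed. The costs are one more table denominator and, because 7.1.2 and 7.1.2.8 instruct sites on recording, a protocol amendment with ethics committee approval (12.1). Given the small effect, the wording could wait for the next amendment made for another reason.

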5.4.5 Replacement of Subjects

Should a subject meet eligibility, but is unable to be scheduled for dosing, that subject will be considered a screen failure. In addition, subjects who are unable to have a tGFR measured by the MediBeacon[®] TGFR Measurement System (due to premature sensor removal, for example) or a major protocol deviation (such as a dosing extravasation) may be replaced to ensure the minimum evaluable sample size is enrolled. All subjects with exposure to MB-102 will be included in the safety analysis.

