6.6 MB-102 Dosing

The dose of 130 mg MB-102 (7.0 mL injection) should be prepared based on instructions provided in the Study Procedure Manual. Final dose calculation should be based on weight and not volume, therefore dosing syringes will be weighed prior to administration. The prepared syringe should be maintained at ambient temperature. MB-102 dosing will be performed in the opposite arm from PK draws whenever feasible.

Administration of MB-102 will be via direct intravenous (IV) injection following angio-catheter placement. Care should be taken to prevent extravasations during dosing. Ideally, a 22 - 24 gauge angio-catheter and 10 mL syringe should be used for administration. Catheter size will be collected.

- Ensure Universal Standard precautions are taken with handwashing and gloving procedures; maintain aseptic technique when handling the prepared syringe
- Check the patency of the placed catheter by injecting a small volume of saline prior to MB-102 dosing
- Administration of MB-102 should be via a steady IV injection (without hard pressure) over 30 60 seconds (smaller bore catheters [24 gauge] may require a slower injection)
- Following MB-102, a 10 mL saline flush should be administered over 30 60 seconds
- The injection site should be observed for swelling or induration or yellow discoloration indicative of a drug infiltration. Drug infiltration may also cause discomfort or pain to the study subject.
- The dosing catheter will be removed after the saline flush is completed.

To avoid extravasation/infiltration:

- Ensure no dislodgement of the needle cannula during venepuncture
- Ensure the back vein wall is not punctured during placement
- Avoid strong pressure on the syringe plunger during saline or MB-102 administration
- Perform a slow injection over the full 30 60 seconds.

If an extravasation occurs, record it as both an adverse event and a protocol deviation. Subjects with evidence of MB-102 or saline extravasations will be discontinued from PK collection and fluorescent measurements but followed for safety. Subjects may be replaced at the discretion of the Sponsor.

The time noted at the completion of MB-102 injection (but prior to the saline flush) is the starttime for the timing of the PK draws.

Following dosing, the syringe will be weighed in order to calculate an accurate dose of MB-102.

6.7 **Post-dose Study Procedures**

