6.9 Follow-up Visit

Subjects will return for a safety follow-up visit approximately 7 +/-3 days after the dosing visit. The following assessments will be performed

- Perform a full or limited physical exam and collect vital signs including temperature (Sections 7.1.2.7 and 7.1.2.8)
- Obtain laboratory tests including chemistry, hematology, and urinalysis (Section 7.1.2.6 and Table 3).
- Record concomitant medications
- Collect adverse events; review ongoing AEs and document resolution (when applicable)

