6.11 Repeat Subjects

Subjects may be re-enrolled in the protocol in the following situations (and if no documented safety concerns regarding exposure to the investigational device or drug):

- When a dose extravasation has occurred
- When there is a device malfunction (sensor falling off during the monitoring period and before a tGFR has been reported)
- Back-up subjects who were not dosed

Stratum 1 subjects must have a minimum of a 3-day wash-out from prior exposure of MB-102 before receiving another dose. Stratum 2 subjects must have a minimum of a 7-day wash-out from prior exposure of MB-102 before receiving another dose

In some cases, the screening visit (if outside the 21-day window) may need to be repeated. Repeat subjects will maintain the same subject ID.

Subjects can be in the study a maximum of two times and only when the above situations have occurred.

7 Efficacy and Safety Variables

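### Section 9.6 ties the safety analyses to single-dose subjects, sections 9.2 and 5.4.5 include everyone dosed, and no rule covers subjects re-dosed under section 6.11

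*Combined protocol and SAP*

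**What the plan says.** Section 9.6 defines treatment emergence for the drug from the first dose and for the device from sensor placement. It closes with "All safety analyses will be done for subjects receiving a single dose of MB-102".

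Section 9.2 sets a wider population: "The safety population will consist of all subjects who are enrolled in the study and have been dosed with MB-102". It also states what that population is for: "The Safety Population will be used for the analysis of all safety variables and baseline characteristics". Section 5.4.5 agrees with it: "All subjects with exposure to MB-102 will be included in the safety analysis".

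Section 6.11 lists three situations in which a subject may re-enter the study. The first is "When a dose extravasation has occurred". The second is a sensor that comes off before the device has reported a tGFR. The third concerns back-up subjects who were never dosed, so only the first two can lead to a second dose. A repeat subject keeps the same ID and may take part at most twice. On timing, "Stratum 1 subjects must have a minimum of a 3-day wash-out from prior exposure of MB-102 before receiving another dose"; for Stratum 2 the minimum is 7 days.

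Two other sections matter here. Section 6.6 says: "If an extravasation occurs, record it as both an adverse event and a protocol deviation", and section 8.3.1 repeats this. Section 6.9 says: "Subjects will return for a safety follow-up visit approximately 7 +/-3 days after the dosing visit".

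**The concern.** The population rules agree only if nobody receives two doses, and section 6.11 provides for exactly that. A programmer working from section 9.6 and one working from section 9.2 could build different safety tables.

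The subjects in dispute are not a random subset. A dosed subject reaches a second dose through an extravasation, which is an adverse event by rule, or through a sensor failure. Such events bear on the second and third study objectives (safety of the drug and of the device). Leaving these subjects out would remove the event that made them eligible for re-dosing, so the reported rates would tend to fall.

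Keeping them without further rules raises a different problem. The second objective concerns one dose, and events from two doses would be counted together.

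**Working it through.** The plan gives no figure to reproduce on this point. The check is a comparison of the sections, then an illustration on stated assumptions.

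**Who is counted**

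| Dosed subject | 9.6 read literally | 9.2 and 5.4.5 |
|---|---|---|
| One dose, no problem | in | in |
| Extravasation or sensor loss, not re-dosed | in | in |
| Extravasation, then re-dosed | out | in |
| Sensor loss, then re-dosed | out | in |

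The readings differ only in the last two rows. Because the ID is kept, a re-dosed subject is one subject with two doses, and the first episode is not a separate single-dose record. The text available does not say which statement prevails.

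**If re-dosed subjects are kept**

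Drug treatment emergence starts at the first dose. An event that begins after dose 2 is therefore treatment-emergent and enters the same table as events after dose 1. The device has its own start, sensor placement, but section 9.6 does not say how two placements in one subject are handled. Section 9.6.1 provides for start and stop dates and times for each event, so the data needed to separate episodes will exist. The rule for using them is missing.

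**Possible size (assumptions only)**

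The document gives no extravasation or re-dosing rate. Section 8.1 lists extravasation among the Pilot 2 injection site reactions but gives no count.

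*Extravasation rate.* Assume 200 dosed subjects with 4 (2%) or 10 (5%) extravasations.
- If half are re-dosed and dropped: 2/198 = 1.0% or 5/195 = 2.6%.
- If all are re-dosed and dropped: 0%.

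*Subjects with any adverse event.* Assume 250 dosed, the Pilot 2 rate of 12.0% (28/234, section 8.1) in everyone without an extravasation, and k subjects re-dosed, each after an extravasation.
- All dosed: [0.12 × (250 − k) + k] / 250.
- Single-dose only: 0.12 × (250 − k) / (250 − k) = 12.0% for every k.

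| k | All dosed | Single-dose only |
|---|---|---|
| 2 | 31.76/250 = 12.7% | 12.0% |
| 5 | 34.40/250 = 13.8% | 12.0% |
| 12 | 40.56/250 = 16.2% | 12.0% |
| 25 | 52.00/250 = 20.8% | 12.0% |

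If only about half of the re-dosing follows extravasation (1, 2, 6 and 12 cases), the all-dosed figures are 12.4%, 12.7%, 14.1% and 16.2%. The Pilot 2 rate may already include some extravasations, in which case these gaps are somewhat too wide.

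**Timing of the follow-up visit**

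The visit window for dose 1 runs from day 7 − 3 = 4 to day 7 + 3 = 10. The Stratum 1 minimum before another dose is 3 days, and 3 < 4. A subject re-dosed on day 3 therefore has the whole dose 1 window after dose 2. The window for dose 2 would then run from day 3 + 4 = 7 to day 3 + 10 = 13, so a visit on days 7 to 10 would lie in both. The document does not say whether one visit may serve both doses. In Stratum 2, with a 7-day minimum, a visit on days 4 to 7 can precede dose 2, but one on days 8 to 10 may not.

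**The case against.** The best defence is that the closing sentence of section 9.6 only names the regimen. The objectives, the synopsis, section 5.1 and section 9.4 all describe the study as single-dose. Section 9.6 itself counts from the first dose, wording that fits with keeping subjects who later receive another. Sections 9.2 and 5.4.5 are explicit about who belongs. This has force. A reader might infer that re-dosed subjects are certain to be excluded, and the documents do not support that. They do show a sentence about all safety analyses, in the section that governs them, that conflicts with two others. The defence also leaves the attribution gap open.

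A reader might also infer that dose 1 loses its laboratory tests, examination and adverse event collection when dose 2 comes early. The documents do not support that either:
- After sensor loss, safety assessments continue for the full 12 or 24 hours (section 7.1.2.5.1).
- Subjects with an extravasation or dislodgement are asked to stay for dosing-day safety assessments and the follow-up visit (section 10.5).
- Baseline procedures before a second dose bring a new physical assessment, vital signs, ECG and laboratory tests (section 6.5).
- Adverse events are collected from sensor placement through the follow-up visit (section 7.1.2).
- Re-enrolment requires that there be no documented safety concern (section 6.11).

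What remains unclear is only how the follow-up visit for dose 1 is obtained.

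Nor would the events vanish from the study record. Extravasations are also protocol deviations, and device and adhesive failures are documented in the eCRF (section 7.1.2.5). The risk is to the adverse event tables. Under the inclusive reading, pooling adds events and hides none.

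**Conclusion.** The concern holds as a contradiction between section 9.6 and sections 9.2 and 5.4.5, together with a missing rule for adverse events across two dosing episodes. It should be corrected, because the subjects in dispute are selected by the very events the safety tables are meant to show.

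The size cannot be stated. The illustrations run from almost no effect to several percentage points and depend wholly on assumed rates. A reader might take the 250 − 188 = 62 enrolments above the evaluable target as a guide to re-dosing. They are room for all non-evaluable subjects, and repeat subjects keep their ID, so that figure neither measures nor bounds it. Section 6.11 only permits re-enrolment, and an extravasated subject who is not re-dosed stays in under either reading. The primary P30 endpoint is unaffected.

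**What to change.** Replace the last sentence of section 9.6 with wording such as:

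*All safety analyses use the Safety Population (all subjects dosed with MB-102). For re-dosed subjects, AEs are attributed to the dosing episode in which they began, and events after the second dose are also shown separately.*

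This aligns section 9.6 with sections 9.2 and 5.4.5 and closes the attribution gap. Restricting the main tables to the first episode, with the second tabulated apart, is another acceptable convention. The choice should be written down before the safety data are summarised, so that the denominator is not picked afterwards.

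The 3-day minimum in section 6.11 and the day 4-10 visit in section 6.9 must also be reconciled, so that it is clear how the follow-up visit for dose 1 is obtained in a Stratum 1 subject re-dosed before that visit. The sponsor decides how.

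The cost is wording and one small table. The reported adverse event rate may be slightly less favourable than under the literal reading.
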